#### 4.5.2 Adverse Events

Individual listings of all AEs will be provided indicating whether the AE is treatmentemergent or treatment-emergent related to study intervention and including AE onset relative to start of treatment, the actual dose (or sham titration) level at the start of the AE, and the duration of the AE.

AEs will be summarized using the MedDRA terms by SOC, HLGT (if feasible) and PT.

The following AEs have been defined as AESIs and are recorded as such:

- AEs suggestive of hepatic injury,
- Syncope/loss of consciousness,
- Acute kidney injury suggested by 2.0-fold increase in serum creatinine or >50% decrease in eGFR.

The number of participants with at least one such event in the following TEAE categories will be given by treatment and total:

- Any AE
- any TEAE,
- any mild, moderate, severe TEAE (maximum intensity),
- any TEAE related to study intervention,
- any mild, moderate, severe TEAE related to study intervention,
- any TEAE related to study procedures,
- any treatment emergent SAE,
- any TEAE leading to death,
- any treatment emergent SAE related to study intervention,
- any TEAE leading to not up-titrating study intervention,
- any TEAE leading to dose reduction of study intervention,
- any TEAE leading to interruption of study intervention,

- any TEAE leading to permanent discontinuation of study intervention, and
- any treatment emergent AESI (also broken down by category of special interest as stated above).

These frequency tables will also be presented broken down by maximum intensity of the TEAEs, where appropriate.

Individual listings will be provided for serious TEAE, deaths, treatment emergent AESI, TEAE leading to study intervention interruption, TEAE leading to not up-titrating study intervention, TEAEs leading to study intervention reduction, and TEAEs leading to study intervention discontinuation.

Participants on active treatment are expected to be up titrated to different dose levels of runcaciguat. Thus, the frequencies of participants with TEAEs will also be presented for each dose level. This summary will be presented for 30, 60, 90, 120 mg of runcaciguat, and a combined placebo group (corresponding to a dose level of zero, i.e., sham titrations will not be handled as different placebo dose levels). Since the exposure times for each dose level will not be comparable, incidences will be calculated with respect to the exposure time in the respective dose level. An AE will be allocated to the dose level on which it started. The number of participants with AEs allocated to a certain dose level will be presented and divided by the exposure time of that dose level considering all participants on that dose level. The result will be multiplied by 100 to present incidences of participants with TEAEs per 100 participant-years. In addition, the analysis will be broken down by titration phase and maintenance phase to check whether TEAEs on a new higher dose level differ from TEAEs on maintenance treatment. The following time windows will be assigned to titration phase and maintenance phase for the respective runcaciguat dose levels:

- 30 mg: Titration phase: week 1 Maintenance phase: week 2-97
- 60 mg: Titration phase: week 2
  - Maintenance phase: week 3-97 Maintenance phase: week 4-97
- 90 mg: Titration phase: week 3
- 120 mg: Titration phase: week 4 Maintenance phase: week 5-97

The table will be repeated summarizing incidences of participants with treatment emergent AESIs.

AEs will be displayed graphically (if feasible) by HLGT, grouped by SOC.

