4.1.1 Part 1 – PK/PD

In Part 1, the randomized participants will be titrated at weekly visits in 30-mg increments to the target dose of 120 mg QD, or the maximum individually tolerated dose. After the titration period, the individually reached highest dose will be maintained until the end of treatment, for the total treatment duration of 48 weeks, followed by a 4-week safety follow-up period. A total of 18 participants are planned to be randomized into Part 1 (12 active; 6 placebo). A schematic study design for Part 1 is provided in Figure 1–1.

In Part 1, additional safety, PK and PD investigations will be performed during the titration phase as described in Table 1-3. On Visits 2 to 6, participants will remain at sites for 4 hours post-dose. During this time, the pulse rate and the blood pressure will be checked and OCT-A will be used to assess retinal perfusion as PD markers. Blood samples will be drawn for population PK and for PK/PD analyses pre-dose and in two post-dose windows.

09 FEB 2023 Page: 29 of 95

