4.1.2 Part 2 – Proof of concept

Recruitment, screening, and randomization of participants for Part 2 of the study is independent from Part 1.

Part 2 of the study is planned to follow the same titration and dosing scheme as Part 1.

In Part 2, the participants will be randomized to either placebo (n = 40) or runcaciguat (n = 40). The participants are planned to be titrated at 30-mg increments to the maximum tolerated dose or sham titrated. Each participant will continue treatment for a total treatment duration of 48 weeks, followed by a 4-week follow-up period.

The 24-week and 48-week data together are intended to derive proof-of-concept and may provide information on the durability of the effect.

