6.3 Measures to minimize bias: Randomization and masking

All participants will be centrally assigned to randomized study intervention using IWRS. Before the study is initiated, the log in information and directions for the IWRS will be provided to each site.

Participants will be randomized to either Placebo or Runcaciguat. Randomization will be stratified by baseline DRSS score (47 or 53). In Part 1, the randomization ratio will be 2:1 runcaciguat: placebo and in Part 2 it will be 1:1.

Potential bias will be reduced by the use of central randomization via the IWRS. The level of masking is presented in Table 6-2.

Table 6-2	Level of masking – Part 1 and 2

	Masked	Unmasked
Participant	•	
Care provider	•	
Investigator	•	
Outcomes assessor	•	
Sponsor study team (except Bioanalytical / PK group)	•	
Sponsor Bioanalytical / PK group		•

PK = pharmacokinetics

The IWRS will be programmed with instructions on how to break / unmask a participant's randomized treatment. In case of an emergency, the investigator has the responsibility for determining if unmasking of a participant's intervention assignment is warranted. If the investigator is unavailable, and a treating physician not associated with the study requests emergency unmasking, the emergency unmasking requests are forwarded to the emergency medical advice 24 hours / 7 day service. Participant safety must always be the first

09 FEB 2023 Page: 40 of 95

consideration in making such a determination. If the investigator decides that unmasking is warranted, the investigator should make every effort to contact the sponsor prior to unmasking a participant's intervention assignment unless this could delay emergency treatment of the participant. If a participant's intervention assignment is unmasked, the sponsor must be notified within 24 hours after the unmasking. Date and reason for the unmasking must be recorded in the source documentation and case report form, as applicable.

Bioanalytics and pharmacometrics staff will be unmasked according to Sponsor's standard operating procedures. Pharmacometrics analysis and report will be done under a separate cover. Bioanalysis and pharmacometrics evaluation might be started prior to database lock: if this is applicable, appropriate measures will be taken to maintain masking of the study team, e.g. data will be stored separately, and members of the study team will not have access to the unmasked data.

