9.2 Sample size determination

The overall planned sample size is displayed in Table 9-1.

Table 9-1 Planned sample size

	Target dose	Part 1	Part 2	Total	
Randomized	Placebo	6	40	46	
	30 mg	-	-	-	
	60 mg	-	-	-	
	90 mg	-	-	-	
	120 mg	12	40	52	
	Overall	18	80	98	
Evaluable*				80	

^{*}minimum evaluable for primary endpoint

The relative contribution of Part 1 and Part 2 to the combined total of N = 98 randomized participants may vary. The assessment of the primary endpoint will include the combined total of all evaluable participants.

If unexpectedly high dropout rates occur (e.g. due to COVID-19), the number of randomized participants may be increased by up to 20%.

The study will use a Bayesian concept for inference, which is based on the posterior probabilities that the research hypotheses are true. Proof of concept shall be defined as fulfillment of the following criteria:

- \geq 90% posterior probability for the hypothesis of clinical activity (i.e. $Pr(\pi_{ACT} > \pi_{PLC} | data) \geq 0.9$)
- $\geq 50\%$ posterior probability for the hypothesis of clinical relevance (i.e. $Pr(\pi_{ACT} > 0.25 | data) \geq 0.5$).

The sample size has been chosen to provide at least 90% probability to obtain proof of concept.

The following assumptions have been used

- True response probability for placebo: 10%
- True response probability for runcaciguat 120 mg: 35%

The response criterion is assumed to be binomially distributed. For the Bayesian evaluation, a Jeffries' prior (i.e. a Beta (0.5;0.5)-prior) has been used. Sample size was determined with a simulation approach using the R environment.

To be able to declare both clinical activity and clinical relevance ≥ 40 evaluable patients are needed in both groups.

98 participants will be randomly assigned to the study intervention such that approximately 80 evaluable participants complete the study. Of 98 participants, 18 participants will be randomized with a ratio of 2:1 to highest runcaciguat dose and placebo for Part 1 (PK/PD). 80 participants will be randomized with a ratio of 1:1 to placebo and runcaciguat for Part 2 (Table 9-1).

09 FEB 2023 Page: 61 of 95

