### 3. Analysis Sets

Final decisions regarding the assignment of participants to analysis sets will be made during the review of study data and documented in the final list of important deviations, validity findings and assignment to analysis sets.

For the purposes of analysis, the following analysis sets are defined in Table 3-1. The same definitions apply for Part 1 and Part 2.

Participant analysis set	Assignment rule	
Full analysis set (FAS)	All participants of the respective study part randomized to treatment who fulfilled in/exclusion criteria.	
Per protocol set (PPS)	All FAS participants of the respective study part without validity findings.	
Pharmacokinetic analysis set (PKS)	All participants of the respective study part with PK information not affected by relevant validity findings and with at least one valid post-dose plasma concentration.	
Safety analysis set (SAF)	All participants of the respective study part who took at least one dose of study intervention.	

It is planned to pool the data of participants from Part 1 and Part 2 for analysis, without further stratification by analysis parts, considering that selection criteria and recruitment time periods were identical and all study procedures in Part 2 were performed also in participants enrolled in Part 1. Participants will be analyzed by their actual treatment to which they were treated for most of the time (i.e., placebo or runcaciguat, irrespective of the planned dose they were planned to be titrated to).

The detailed definitions of validity findings and the assignment of participants to the analysis sets will be based on the ACIR document.

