#### 4.5.5 Vital signs

- SBP, DBP
- Heart rate

The measurements at each visit during the titration phase will be summarized for each time point descriptively by parameter including absolute changes from baseline. Arithmetic mean plots including standard deviation over time will be presented.

Frequencies of participants with a decrease in SBP from the previous visit by >30 mmHg will be presented. In addition, frequencies for the following combinations of the above criteria will be summarized reflecting the up-titration criteria:

- $\geq$ 105 mmHg SBP *and*  $\leq$ 30 mmHg decrease from previous visit (dose increase),
- ≥105 mmHg SBP *and* >30 mmHg decrease from previous visit *or*

<105 mmHg and  $\geq$ 90 mmHg SBP (dose maintenance),

• <90 mmHg SBP (dose decrease to previous level).

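### TEAE counts are pooled by arm across two Parts with different allocation ratios and different safety monitoring; if Part 1 detects more events, this adds a small spurious excess on runcaciguat that analysis by Part would remove

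*SAP*

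**What the plan says.** **Allocation.** Protocol 6.3: "In Part 1, the randomization ratio will be 2:1 runcaciguat: placebo and in Part 2 it will be 1:1". Protocol 4.1.1 and 4.1.2 plan 12 runcaciguat and 6 placebo participants in Part 1, and 40 per arm in Part 2. The mix is not fixed. Protocol 9.2: "The relative contribution of Part 1 and Part 2 to the combined total of N = 98 randomized participants may vary".

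**Monitoring.** Protocol 4.1.1 on Part 1: "On Visits 2 to 6, participants will remain at sites for 4 hours post-dose". In Table 1-2, blood pressure, pulse and triplicate ECG are scheduled pre-dose, at 1-2 h and at 2-4 h at each of these five visits. In Table 1-3, Part 2 has one set per visit, taken pre-dose, with a single ECG (Protocol 8.2.3). From Visit 7 both Parts follow Table 1-4, with the same blood pressure, pulse and ECG schedule.

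**Pooling.** SAP 3 pools the Parts and does not stratify by Part. One reason it gives is that "all study procedures in Part 2 were performed also in participants enrolled in Part 1".

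**Adverse event tables.** SAP 4.5.2: "The number of participants with at least one such event in the following TEAE categories will be given by treatment and total". Further breakdowns are by intensity, dose level, and titration or maintenance phase. The only endpoints that the SAP analyses separately by Part are the OCT and OCT-A parameters (SAP 4.4.3).

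**Blood pressure categories.** SAP 4.5.5: "Frequencies of participants with a decrease in SBP from the previous visit by >30 mmHg will be presented". It does not say which reading counts when a visit has three.

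**The concern.** Part is tied to arm by the allocation ratios and to intensity of observation by the schedule. A crude arm comparison that ignores Part therefore mixes any drug effect with a difference in how closely participants were watched.

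The reason given in SAP 3 runs the wrong way for harms. It is true that Part 1 participants had every Part 2 procedure, but detection depends on the checks that Part 1 had and Part 2 did not. Those checks can generate adverse events: under Protocol 10.3.1, a vital-sign or ECG abnormality judged clinically significant counts as one.

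TEAE frequency is the endpoint of the secondary objective. The extra checks are aimed at blood pressure fall with compensatory tachycardia, which Table 2-2 of the Protocol lists as a potential risk of the drug.

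**Working it through.** **1. Arm totals (Protocol Table 9-1, SAP Table 5-1).** Runcaciguat 12 + 40 = 52; placebo 6 + 40 = 46. Both agree with the tables.

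**2. Share of each arm that comes from Part 1.** 12/52 = 23.1%; 6/46 = 13.0%. Gap = 0.2308 - 0.1304 = 0.100.

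**3. Pooled difference with no drug effect.** Let p1 and p2 be the proportions with a recorded TEAE in Parts 1 and 2, equal in both arms within a Part.

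- Runcaciguat: A = (12 p1 + 40 p2)/52
- Placebo: P = (6 p1 + 40 p2)/46
- A - P = 0.100 × (p1 - p2)

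The documents give neither p1 nor p2, so the rates below are assumptions. The standard error is the square root of A(1-A)/52 + P(1-P)/46.

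| p1 | p2 | Runcaciguat | Placebo | Difference (points) | Ratio | SE (points) |
|---|---|---|---|---|---|---|
| 30% | 20% | 22.3% | 21.3% | +1.0 | 1.05 | 8.4 |
| 30% | 5% | 10.8% | 8.3% | +2.5 | 1.30 | 5.9 |
| 50% | 20% | 26.9% | 23.9% | +3.0 | 1.13 | 8.8 |
| 80% | 60% | 64.6% | 62.6% | +2.0 | 1.03 | 9.7 |

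The spurious difference is between 0.12 and 0.42 of a standard error in these cases.

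**4. How much more observation there is.** Count scheduled blood pressure and pulse sets.

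- Visits 2 to 6: Part 1 has 5 × 3 = 15, Part 2 has 5. Per participant: (12×15 + 40×5)/52 = 7.31 on runcaciguat and (6×15 + 40×5)/46 = 6.30 on placebo, +16%.
- Visits 2 to 16, the span relevant to TEAEs: the ten visits from 7 to 16 add 10 sets in both Parts, giving 25 and 15. Per participant: (12×25 + 40×15)/52 = 17.3 and (6×25 + 40×15)/46 = 16.3, +6%.

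**5. Effect of stratifying by Part.** The Mantel-Haenszel weights are 12×6/18 = 4 and 40×40/80 = 20. With no drug effect the difference within each Part is zero, so the stratified difference is (4×0 + 20×0)/24 = 0 for any p1 and p2.

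**6. If the mix changes.** With 30 of 98 in Part 1 (20:10, leaving 34:34 in Part 2), the gap is 20/54 - 10/44 = 14.3 points instead of 10.0.

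**The case against.** The strongest reply is that this is too small to matter and that no planned inference is affected. SAP 4.5.2 plans counts, listings and exposure-adjusted incidences, with no risk difference or test. Extra readings are also not extra adverse events: a reading must be judged clinically significant, participants report events themselves (Protocol 8.3), open-ended questioning is preferred (8.3.2), and events are recorded throughout in both Parts. Masking should keep detection even between arms within a Part. The post-dose checks end at 4 hours, whereas Protocol 2 puts peak concentration at about 10 hours. Symptomatic events such as syncope can come to light without a scheduled reading. On SAP 4.5.5, the titration decision sits in the pre-dose column of Table 1-2, so pre-dose is the natural reading. Finally, the table specifications are a separate document, so the absence of an adverse event table by Part is shown only for the SAP text.

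All of this stands as a limit on size. It does not remove the confounding of arm with Part, and readers will compare the two columns of a by-treatment table whether or not a test is planned.

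Three stronger readings are tempting and should not be drawn:

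- *A real tolerability signal could not be told apart from closer observation.* The calculated bias is well under one standard error, and listings by participant would allow a check.
- *The bias always runs against runcaciguat.* That requires a higher event rate in Part 1. The documents give no rates by Part, and the Parts use different kinds of site (Protocol 1.1), which could shift reporting either way.
- *Runcaciguat participants are observed 16% more, or show 1.77 times the events (23.1/13.0).* The first figure covers Visits 2 to 6 only; over the TEAE window it is 6%. The second applies only to an event found solely by post-dose checks, and the documents identify none.

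**Conclusion.** The point holds as a low-severity weakness. The planned TEAE table confounds arm with Part, and the justification for pooling does not address the extra Part 1 checks. At the planned 12:6 and 40:40, the spurious difference is one tenth of the difference in detection between Parts: about 1 point for 10 points of extra detection in Part 1 and 3 points for 30. The direction rests on Part 1 detecting more, which is plausible from the schedule but not established. The effect is most relevant to hypotension, tachycardia and ECG findings during titration, where the schedules differ, and to the titration-phase incidences in SAP 4.5.2. For overall TEAE frequency it is minor.

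**What to change.** - **SAP 4.5.2:** keep the pooled counts. Add the TEAE and AESI overview by Part. Wherever arms are compared, give a Part-stratified (Mantel-Haenszel) risk difference, at least for hypotension, tachycardia, dizziness and syncope terms in the titration phase.
- **SAP 4.5.5 and 4.5.6:** state that the pooled systolic blood pressure categories and ECG-finding frequencies at Visits 2 to 6 use the pre-dose time point only. Report the Part 1 post-dose readings separately.

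The cost is SAP wording and a few extra tables, with no new data. The Part 1 table, at 12:6, will be imprecise, and the stratified difference will be slightly less precise than the crude one.

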To assess the efficacy, the retinal morphology will be investigated by 7-field color fundus photography (CFP) supported by 7 Field FA images for the assessment of the DRSS by a central reading center. Two-step DRSS improvement at 48 weeks of treatment will be the primary efficacy endpoint. Additional DRSS assessments are done after 12 and 24 weeks of treatment. In addition, vision-threatening complications will be recorded throughout the study and assessed as secondary efficacy endpoint.

During the course of the study, 16 visits are planned, including the screening visit (Visit 1) and the end-of-study visit (Visit 16). Visit intervals are weekly during the first 4 weeks, while the dose of runcaciguat (or placebo) is titrated to the target dose, then fortnightly for the next 4 weeks and then every 4 weeks up to Week 25 (Visit 12). The subsequent visits, up to end of treatment in Week 49 (Visit 15), will be at 8-week intervals. The end-of-study visit, Visit 16, will take place 4 weeks later.

Number of participants:

A combined total of approximately 98 participants for Part 1 and 2 will be randomly assigned for an estimated total of \geq 40 participants per intervention group evaluable for primary endpoint assessment, as defined in Section 9.2. The estimated screen failure rate is approximately 50%.

Intervention groups and duration:

Participants are randomly assigned to one of two study arms. Assignment will be masked, as detailed in Section 6.3. After providing informed consent, participants will be screened (Visit 1) and within up to 4 weeks, eligible participants will be randomized and treatment will be initiated at Visit 2. During the initial four weeks, treatment will be titrated to the target dose of 120 mg runcaciguat or matching placebo. Treatment will start at 30 mg runcaciguat or placebo once daily for the first week. If well tolerated, the dose will be increased to 60 mg runcaciguat or placebo at Visit 3 in the second week of treatment, then to 90 mg runcaciguat or placebo at Visit 4 in the third week of treatment, and finally to 120 mg runcaciguat or placebo at Visit 5.

In case of intolerability (see Section 6.5.1) treatment may continue without up-titration or the dose may be reduced by one titration step.

Treatment will continue at the highest tolerated dose until completion of 48 weeks of treatment if tolerated, or until development of a vision threatening complication or development of PDR.

[figure not shown]

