#### 4.5.1 Treatment Compliance, Duration and Exposure

Tables will be presented for the FAS and PPS.

Frequency tables and summary statistics will be presented for total dose, treatment dose per week, and treatment duration (absolute duration and frequencies with weekly intervals). In addition, treatment compliance will be summarized presenting the percent of tablets that were actually taken out of the planned number of tablets. Frequencies of participants showing compliance <80%, 80-120%, and >120% of the planned tablets will be presented.

The frequencies of dose modifications will be presented by treatment group and visit, especially to assess the escalation, maintenance, reduction, and withdrawal of doses, including the reasons for maintenance, reduction, or withdrawal. Furthermore, the frequency of participants being treated on a certain dose level will be presented by treatment group, visit and dose level to assess the titration level being reached during up-titration and in the maintenance phase.

A listing with the actual dose levels or sham-titration levels for each visit will be presented to get an overview of the individual titration schemes.

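### SAP 4.5.2 sets runcaciguat dose levels that mostly cover one early week against placebo averaged over 48 weeks, and names no placebo window for the titration/maintenance split

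*SAP*

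**What the plan says.** SAP 4.5.2 plans TEAE incidences for 30, 60, 90 and 120 mg and for a single placebo group, with the rule that "sham titrations will not be handled as different placebo dose levels". An AE belongs to the dose level on which it started. The rate is the number of participants with such an AE divided by the exposure of everyone on that level, times 100.

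The analysis is then broken down by phase: "The following time windows will be assigned to titration phase and maintenance phase for the respective runcaciguat dose levels". The windows begin "30 mg: Titration phase: week 1 Maintenance phase: week 2-97", then "60 mg: Titration phase: week 2" and "90 mg: Titration phase: week 3", with week 4 for 120 mg and 120 mg maintenance from week 5. No window is given for placebo. The stated aim of the split is to see whether TEAEs on a newly reached dose differ from those on maintenance. The table is repeated for AESIs.

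The printed maintenance windows end at week 97, although treatment lasts 48 weeks (SAP 1.2). The two need to be reconciled; 48 weeks is used below.

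Two other provisions matter. Protocol 1.1 states "Visit intervals are weekly during the first 4 weeks", with 8-week intervals after Week 25. SAP 4.5.1 states "A listing with the actual dose levels or sham-titration levels for each visit will be presented", and the AE listings in SAP 4.5.2 carry onset relative to treatment start and the sham level at AE start.

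**The concern.** Under protocol 6.5.1 a participant who titrates as planned is on 30 mg in week 1, 60 mg in week 2, 90 mg in week 3 and 120 mg from week 4. Dose level and time on study are therefore nearly the same variable in the runcaciguat columns, and AE capture is likely to vary along that axis. Visits are densest early. Two of the three AESI categories, hepatic injury and acute kidney injury, are detected largely from blood samples taken at visits.

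A placebo rate averaged over 48 weeks cannot show how much of an early excess would have occurred without drug. The titration-versus-maintenance contrast within runcaciguat has the same weakness, since a fall from early to late could be adaptation to the drug or ordinary decline in reporting. Protocol 4.3 expects acute haemodynamic effects to attenuate with repeated dosing, so a falling rate could easily be read as confirmation.

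**Working it through.** The documents give no TEAE rate and no early-to-late ratio, so there is no plan figure to reproduce. The check applies the SAP's own rate to two arms with the same AE hazard, that is, with no drug or dose effect.

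**Inputs from the documents**
- Rate: participants with at least one AE starting in the window ÷ total exposure in the window × 100. Exposure is not stopped at the first AE (SAP 4.5.2).
- Windows: weeks 1, 2, 3, 4, and weeks 5-48 for 120 mg maintenance; placebo weeks 1-48.
- One week = 7/365.25 = 0.019165 years; 44 weeks = 0.8433; 48 weeks = 0.9199.
- Randomized: 52 runcaciguat, 46 placebo (SAP Table 5-1).

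**Assumptions:** full titration on schedule, no dropout, 50% TEAE incidence at 48 weeks, and a weekly hazard in weeks 1-4 that is m times the later hazard h.

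**Formulas**
- h = −ln(1 − 0.5)/(4m + 44) = 0.6931/(4m + 44)
- Titration-week rate = 100 × (1 − exp(−m·h))/0.019165
- 120 mg maintenance rate = 100 × (1 − exp(−44h))/0.8433
- Pooled placebo rate = 100 × 0.5/0.9199 = 54.4

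For m = 2: h = 0.6931/52 = 0.01333; 1 − exp(−0.02666) = 0.02631; rate 137.3; 137.3/54.4 = 2.5.

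| m | Each titration week, per 100 PY | Ratio to pooled placebo | 120 mg maintenance (ratio) |
|---|---|---|---|
| 1 | 74.8 | 1.38 | 55.8 (1.03) |
| 1.5 | 107.4 | 1.98 | 54.2 (1.00) |
| 2 | 137.3 | 2.53 | 52.6 (0.97) |
| 3 | 190.2 | 3.50 | 49.8 (0.92) |

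**Two sources.** The time effect alone, as a ratio of hazards, is 48m/(4m + 44) = 1.44, 1.85 and 2.57 for m = 1.5, 2 and 3. The remaining factor, about 1.4, is the counting rule: a participant counts once per window, so with uncensored exposure a long window gives a lower rate than a short one. It appears alone in the m = 1 row.

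**Sensitivity to the assumed incidence.** From 30% to 80%, the titration-week ratio runs from 1.18 to 1.98 (m = 1), 2.2 to 3.6 (m = 2) and 3.0 to 5.0 (m = 3). Maintenance at m = 2 runs from 0.95 to 1.01.

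**Declining reporting.** With multipliers 4, 3, 2 and 1.5 in weeks 1-4 and 50% incidence, the rates are 259 (30 mg), 195 (60 mg), 131 (90 mg) and 99 (120 mg titration), or 4.8, 3.6, 2.4 and 1.8 times pooled placebo; 120 mg maintenance is 0.94 times. The false gradient is inverse.

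**With placebo cut into the same windows,** every ratio in these scenarios is 1.00.

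**Precision.** Runcaciguat, one week: 52 × 0.019165 = 1.00 PY, so one participant moves the rate by about 100 per 100 PY. Placebo, one week: 46 × 0.019165 = 0.88 PY, about 113. Pooled placebo: 46 × 0.9199 = 42.3 PY, about 2.4.

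**The case against.** The strongest reply is that the SAP nowhere says the one-week windows are set against whole-period placebo. The rule on sham titration concerns dose levels, not time, and the table specifications are in a separate document that may give placebo phase columns. This stands: the missing phase split for placebo is inferred from the single placebo group and the runcaciguat-only windows. It does not rescue the unsplit dose-level table, where 30, 60 and 90 mg still face placebo averaged over 48 weeks.

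The stated aim of the split is a contrast within runcaciguat, not against placebo. That also stands, but such a contrast still needs a placebo counterpart to separate dose from time.

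AEs are allocated by start date, so denser visits need not move onsets, and no document gives an early-to-late ratio. The multipliers are indeed assumptions. For laboratory-detected events, though, the recorded onset is likely to follow the sampling schedule.

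Randomized information on titration tolerability exists elsewhere. SAP 4.5.2 counts TEAEs leading to no up-titration, reduction, interruption or discontinuation by treatment, and SAP 4.5.1 shows dose modifications by treatment group and visit. This confines the problem to one descriptive table and its AESI repeat.

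A reader might infer that the table would manufacture a rising dose response. The calculation does not show this: a common early multiplier gives equal ratios in all four titration weeks, and declining reporting gives an inverse gradient. A reader might also infer that the table drives titration of follow-up compounds. Protocol 2.1 names dose range and treatment duration, and does not mention this table.

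**Conclusion.** The concern holds in a limited form. As specified, the dose-level table confounds dose with time on study, and the titration-versus-maintenance contrast has no stated placebo analogue. With no drug effect and an assumed 50% incidence, titration weeks would read about 2.0 to 3.5 times pooled placebo for early multipliers of 1.5 to 3, partly through the counting rule. Maintenance would read close to placebo (0.97 at a multiplier of 2). If reporting declines over weeks 1-4, the inverse false gradient could mask a true dose response.

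The size rests on assumed incidence and multipliers, full titration and no dropout; the structural gap does not. It would be wrong to conclude that the trial's safety comparison is compromised. Whole-period TEAE tables by arm compare like with like, and the proof-of-concept decision does not use this table.

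**What to change.** In SAP 4.5.2, state that the combined placebo group will be tabulated over the same calendar windows (weeks 1, 2, 3, 4 and week 5 to end of treatment) in both the TEAE and the AESI tables. State also that each runcaciguat window, and the titration-versus-maintenance contrast, will be read against placebo in the same window. Matching windows also give both arms the same window length, which removes the counting-rule excess from the between-arm reading when there is no effect. Because the 30, 60 and 90 mg maintenance windows start at weeks 2, 3 and 4, either break them at week 5 too or add placebo rows with those start weeks.

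Tabulating placebo by sham level is not an adequate substitute unless it is also split by phase, since sham 120 mg can run from week 4 to week 48.

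The cost is a sentence in the SAP and extra placebo columns, built from onset times already listed. The drawback is imprecision: about 0.9 participant-years per one-week placebo window, against about 1.0 in the runcaciguat windows the SAP already tabulates. The table should be labelled descriptive.
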